## **Appendix 1: Study Devices and Risk Assessment**

### **Background**

The active vestibular nerve stimulation (VeNS) device is being made bespoke by i4 Product Design and a Risk Assessment is detailed below. It will administer a 0.5Hz square wave stimulation up to a maximum current of 1mA. A binaural placement of the electrodes will be used, which means an electrode will be placed on the skin overlying each mastoid process. The battery (4.25V) powered control unit which connects to deliver the stimulation will rest in front of the subject and be connected to the electrodes via cables.

### **Risk Assessment**

In terms of this amendment the following risk assessment was also carried out for vestibular nerve stimulation devices that can deliver up to 1mA. Under the guidance for IRBs from the FDA a device will be determined to be non-significant risk (NSR) if it does not meet the definition of a significant risk (SR) device (see <https://irb.ucsd.edu/device.pdf>). A SR device is

one which meets at least one of the following criteria:

- a. The device is intended as an implant.
- b. The device supports or sustains human life.
- c. The use of the device is of substantial importance in diagnosing, curing, mitigating, or treating disease, or preventing impairment of health.
- d. The device could cause significant harm to any subjects.
- e. The subject must undergo a procedure as part of the device study.
- f. The device appears on the FDA list of significant risk devices.
- g. The study or any of the study procedures could cause harm to the subjects which:
  - i. could be life threatening;
  - ii. could cause permanent impairment of a body function;
  - iii. could cause permanent damage to body structure;
  - iv. or could necessitate medical or surgical intervention to preclude permanent impairment of a body function or preclude permanent damage to body structure.

As the device is not implanted, no procedure is required to use it, it does not support or sustain life and it is not on the FDA list of significant risk devices, criteria a, b, e and f clearly do not apply. Regarding criterion c, the aim of this study is to investigate whether vestibular stimulation can, in conjunction with lifestyle interventions, assist with fat loss. It may be the case that VeNS has such a role, but it is unlikely that this will be of “substantial importance in … curing, mitigating, or treating disease, or preventing impairment of health.” Thus criterion c does not apply.

This then leaves criteria d and g, which both pertain to users suffering significant harm from the device. When the device is turned on it will start at 0mA and the current can then be increased in 0.1mA increments up to 1.0mA. The waveform is a bipolar rectangular shape with 50% duty cycle and – i.e. half the time no current is being delivered. There is also a hardware interlock to ensure the device cannot be switched on when the charging cable is being used. Please note the device is battery, and not mains, powered.

The devices are placed on the head in a manner analogous to headphones, and the VeNS devices will deliver a small electrical current (1.0mA or less) to the skin behind the ears over the mastoid processes. The device can only be used for up to one hour a day, and after being used for this time period the device will automatically lock out until the next day. Delivery of electrical current to the skin over the mastoid region is known to activate all five components of the vestibular apparatus, but lower level currents (below 3mA) are thought to particularly activate the two otolith organs responsible for detecting linear acceleration and gravity (Zink et al., 1998). It is these otolith organs that, from the animal studies, are particularly associated with a reduction in body fat. This technique – known as bilateral bipolar vestibular stimulation – has been known about since the 19th century and is known to be safe, though skin irritation behind the ears can occasionally occur (Fitzpatrick & Day, 2004).

More recently Paneri et al. (2015) reviewed the safety of repeated sessions of transcranial electrical stimulation (tES), a term that they use to encompass both the transdermal electrical modulation of cranial nerves (i.e. as in VeNS) and transcranial direct current stimulation (tDCS) of the cerebral cortex. Based on studies of tES on patient groups with depression (Brunoni et al., 2013) and migraine (Magis et al., 2013), and an array of studies of tES on normal volunteers (Brunoni et al., 2011; Kessler et al., 2012; McIntire et al., 2014; Morales-Quezada et al., 2015; Nitsche et al., 2003; Poreisz et al., 2007; Raimundo et al., 2012; Russo et al., 2013; Tadini et al., 2011), together with theoretical assessments of tES (Bikson et al., 2009; Brunoni et al., 2012), they commented that the “safety and tolerability profile previously accumulated regarding extended use of tES in clinical populations is compelling and supports a low-risk or non-significant risk designation” (Paneri et al., 2015).

Paneri et al. (2015) also assessed the safety and tolerability of repeated tES across time in a group of 100 volunteers who were split into three groups. The first group received sham stimulation, the second tES at 2mA, and the third pulses of tES at between 5 to 7 mA (this is notably higher than the 1mA maximum we are proposing to use). A total of 1905 treatment sessions were carried out in total across the three groups. The authors report no serious adverse events in any treatment condition, and that the common side effects were restricted to skin tingling, itching, and mild burning. Moreover, the incidence of these events were not statistically

higher in the tES groups (Paneri et al., 2015). These mild skin sensations were not associated with withdrawal from the study and the authors report they became less salient after the first few sessions. Other adverse events, such as headache, were rare (<5%) and statistically indistinguishable across the three groups. Paneri et al. (2015) concluded that the “repeated use of limited output tES across extended periods, is well tolerated and poses no significant risks to healthy subjects, as previously observed in clinical studies”.

This conclusion is in keeping with the findings of Wilkinson et al. (2009), who reported on a stroke patient who received repeated VeNS sessions as part of his rehabilitation therapy. The authors observed no adverse events during stimulation over 5 consecutive daily sessions of VeNS at 1mA for 30 minutes per day. Utz et al. (2011) studied the adverse effects of 255 VeNS sessions at 1.5mA (again higher than the 1mA we propose to use) in 55 stroke patients and 30 healthy controls. They found only a few mild adverse effects, with the most common being slight itching (mean 10.2%) and tingling (mean 10.7%) underneath the electrodes. They concluded that VeNS induces “very few and mild adverse effects in healthy and persons with stroke and [is] safe” (Utz et al., 2011). There is thus a body of literature supporting the safe usage of both tES and specifically VeNS devices delivering at least 1mA in stimulation.

Similarly, in February 2016, Halo Neuroscience, a company based in San Francisco, released additional data on the safety of tES; on this occasion for a 2mA tDCS device used on 1010 subjects. They state that “there were zero reports of burn or seizure activity across all 1010 subjects, zero serious or unexpected adverse effects and zero withdrawals due to adverse events other than unpleasant sensation”. They conclude that their tES study showed “a favorable safety profile and [was] associated with a very low incidence of adverse events, with no unexpected or serious adverse events”.

Specific measures taken to reduce the incidence of skin irritation are the 27mm diameter of the electrodes, which are themselves hypo-allergenic, and the 50% duty cycle (i.e. half the time no current at all is being delivered), and the maximum current of 1.0mA. This means that the

---

 <https://halo-website-static-assets.s3.amazonaws.com/whitepapers/safety.pdf>

maximum phase current that can be delivered is only 500 $\mu$ C. In conclusion, there is not a significant risk of harm from using the device, and as such criteria d and g do not apply. Thus as the device does not meet the criteria of a SR device it is a NSR device.

Based upon the statistical power calculations, the aim is to enroll a total of 20 subjects. There will be no exclusion from the study on the basis of race, socioeconomic status, language spoken, or ethnicity.

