### **Stimulation Protocol for Both Active and Sham Devices**

Subjects will have the skin behind their ears cleaned with a disposable alcohol wipe before applying the device. The electrodes that will be used are 25mm in diameter hydrogel electrodes, which are hypo-allergenic. The devices will physically appear identical on the outside and both examiners and subjects will be blinded as to whether the device is active or "sham" control.

The devices will be brought in charged and no charging will take place during their usage in the study. Prior to the session subjects will be counseled that they may or may not experience a

rocking sensation during the stimulation and that not everyone can perceive the vestibular stimulation. This is true and also necessary to prevent subjects distinguishing between the active and sham devices.

There are buttons on the outside of the devices that allow their outputs to be tuned up or down. When initially powered up the devices do not deliver any current. The active device increases its output to the subject in 0.1mA increments. The sham device will discharge its current into an internal resistor rather than the subject.

The devices will be operated by the member of the research team, and over the course of minute or so they will turn it up to a level that the subjects say they are comfortable with for the 45-minute stimulation period. Afterwards subjects will have a little aloe vera gel applied to where the electrodes were, as this is thought to be particularly effective in preventing any skin irritation by VeNS.

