## **RISK MANAGEMENT**

### Risks Related to Vestibular Nerve Stimulation (VeNS)

1. Any potential subjects a history of irritation to the skin behind the ear will be excluded
2. Hypoallergenic hydrogel electrodes of 25mm diameter will be used in order to minimize the likelihood of skin irritation.
3. Subjects will be asked to apply aloe vera gel to minimize any skin irritation after using the device.
4. Prior to the beginning of the study the possible discomforts of VeNS will be described to the participant in lay language, and the investigator will make sure that the subject understands what will happen when using the device.

5. The usage of the device is limited to 45 minutes and a member of the experimental team will oversee.
6. Usage is voluntary, and subjects will be informed at the beginning of the study that they may withdraw at any time, for any reason, with no negative repercussions.
7. Subjects will be warned about the sensation of disequilibrium which may occur and will only be using the device while seated.
8. The maximum current the device can deliver is 1.0mA but there is no requirement for the subjects to use it at this level. Instead they will be asked to indicate when the experimenter has reached a level that is comfortable. The minimum setting is 0.1mA and the current can be increased in 0.1mA increments.
9. If subjects find the sensation invoked at the level the current is set, to be uncomfortable (e.g. in terms of nausea or disequilibrium) then they can ask for a lower, and more comfortable, stimulation level.
10. The subjects can take off the devices at any point they wish.

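### Does the 27 mm electrode diameter in the device risk assessment, against 25 mm elsewhere in the protocol, undermine the non-significant-risk conclusion?

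*Combined protocol and SAP*

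**What the plan says.** The electrode diameter appears in three places.

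- Protocol, Stimulation Protocol for Both Active and Sham Devices: "The electrodes that will be used are 25mm in diameter hydrogel electrodes, which are hypo-allergenic".
- Protocol, Risk Management, Risks Related to VeNS, item 2: "Hypoallergenic hydrogel electrodes of 25mm diameter will be used in order to minimize the likelihood of skin irritation".
- Appendix 1, Risk Assessment, near its end: "Specific measures taken to reduce the incidence of skin irritation are the 27mm diameter of the electrodes". The same sentence also counts the hypo-allergenic material, the 50% duty cycle and the 1.0 mA ceiling as protective measures. The text then gives a maximum of 500 µC per phase and concludes that criteria d and g (significant harm) do not apply.

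Earlier in the same assessment, in answer to criterion c, the text states that "the aim of this study is to investigate whether vestibular stimulation can, in conjunction with lifestyle interventions, assist with fat loss". This trial has two single-session visits with indirect calorimetry and no lifestyle component.

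**The concern.** A named safety measure has two values in current text, and the larger one sits in the argument for the device's risk class. At a fixed current, a smaller electrode concentrates that current on less skin. If subjects wear 25 mm electrodes, the appendix describes a larger contact area than they actually have. Skin irritation is the first risk the protocol lists for VeNS. The reference to lifestyle interventions adds to the suspicion that the assessment was written for a different study or device set-up. If so, the review board may have judged a configuration that is not the one in use.

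**Working it through.** **Inputs.** The diameters are 25 mm (stimulation protocol; risk management, item 2) and 27 mm (Appendix 1, Risk Assessment). On current, risk management item 8 says "The maximum current the device can deliver is 1.0mA but there is no requirement for the subjects to use it at this level". Appendix 1, Background, says "It will administer a 0.5Hz square wave stimulation up to a maximum current of 1mA". Appendix 1, Risk Assessment, says "The waveform is a bipolar rectangular shape with 50% duty cycle".

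**Step 1: the plan's own figure.** Charge per phase = current × phase duration.

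- A frequency of 0.5 Hz gives a period of 1/0.5 = 2 s.
- A 50% duty cycle gives 2 × 0.5 = 1 s of current per period.
- Two polarities share that time, so each phase lasts 1/2 = 0.5 s.
- 1.0 mA × 0.5 s = 0.5 mC = 500 µC.

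This matches the stated value (the appendix calls it a phase current, but the unit is one of charge). Diameter does not enter the calculation, so the figure is the same for either electrode.

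**Step 2: what the diameter does change.** Assume circular electrodes whose whole face conducts; the documents do not say this. Area = π(d/2)².

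| | 25 mm | 27 mm |
|---|---|---|
| Area | π × 1.25² = 4.91 cm² | π × 1.35² = 5.73 cm² |
| Density at 1.0 mA | 1/4.909 = 0.204 mA/cm² | 1/5.726 = 0.175 mA/cm² |
| Charge density at 500 µC | 500/4.909 = 102 µC/cm² | 500/5.726 = 87 µC/cm² |

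- Going from 27 mm to 25 mm, density rises by (27/25)² − 1 = 16.6%.
- Measured against the 25 mm value, the 27 mm density is lower by 1 − (25/27)² = 14.3%. If 25 mm is in use, 14.3% is the size of any implied understatement.
- The ratio is the same at every setting from 0.1 to 1.0 mA.
- If both diameters are rounded to the nearest millimetre, the increase lies between (26.5/25.5)² − 1 = 8% and (27.5/24.5)² − 1 = 26%.

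**Step 3: does the conclusion depend on it?** The assessment quotes no current density and sets no limit on it, so there is no stated value for a new density to contradict and no threshold for it to cross. The appendix describes its supporting studies by current: 1 mA in a single stroke patient, 1.5 mA over 255 sessions, 2 mA and 5 to 7 mA in a 100-volunteer tolerability study, and 2 mA in 1010 subjects. Electrode size is not mentioned for any of them. Criteria d and g concern significant harm, such as life-threatening events or permanent impairment or damage. Diameter is offered only for the lesser matter of skin irritation, as one of four measures.

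**Step 4: is the skin argument made elsewhere?** Yes. Risk management item 2 makes it at 25 mm. The same section adds aloe vera gel, a current set to comfort, reduction on request and removal at will. Exclusion criterion 3 keeps out people with relevant skin conditions.

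**The case for a change.** The strongest case for acting is that this is more than a stray digit. Both the risk-management section and the appendix put the diameter forward as a safeguard, with different values, and a review board reading them cannot tell which electrode it assessed. The lifestyle sentence does not fit this trial and forms part of the dismissal of criterion c. Appendix 1 also describes the device both as a cabled control unit resting in front of the subject and as something worn like headphones. Together these suggest text carried over from other work, and correcting it costs only wording.

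Much of this stands. The contradiction is genuine, unexplained and not an artefact of redaction, and the lifestyle sentence is wrong for this trial. What does not stand is the step from there to a weakened risk classification. The appendix matches the protocol on the 1.0 mA maximum, the 0.1 mA increments, the zero output at start-up and the hypo-allergenic material, so a different configuration is an inference and not a demonstrated fact. The two descriptions of the device are not necessarily incompatible. The lifestyle sentence concerns criterion c and has no bearing on electrode size or on criteria d and g.

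**Conclusion.** This is a clerical inconsistency, and no change to the plan follows. The three statements of diameter must be reconciled with the electrode actually supplied, and the aim sentence in the appendix should be tidied at the same time. The documents do not establish which diameter is correct, and this review does not choose one. The two sections that direct conduct of the sessions agree with each other, so staff following the protocol have a single figure to work from.

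The physical effect is modest: density is about 17% higher at 25 mm than at 27 mm (8% to 26% allowing for rounding), provided that nominal and conducting diameters coincide. It crosses no limit the documents set and leaves the 500 µC figure untouched. The current ceiling, the duty cycle and the cited studies carry the non-significant-risk reasoning at either size, and nothing in the documents shows that the conclusion would differ. Endpoints, randomisation, sample size, alpha and analysis are unaffected.

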## **STATISTICAL ANALYSIS PLAN**

## 1.1 Specific Aims

The aim of this study is to evaluate whether non-invasive electrical vestibular nerve stimulation (VeNS) causes a change in fat consumption in humans as measured using indirect calorimetry.

## 1.2 Analysis Plan and Sample Size Calculation

To account for potential period effects, a cross-over design will be used to assess the effect of VeNS on fat consumption. Subjects will be randomized to either the Sham VeNS sequence or VeNS Sham-sequence. To eliminate the effect of period and sequence effects, standard cross-over design analysis will be performed with an independent samples t-test of differences between the first and second measurement by sequence (Sham → VeNS or VeNS → Sham).

When  $n = 10$  subjects data have been collected, we will perform an interim analysis of the primary aim. Our only considerations will be whether to stop the study to reject the null hypothesis or to continue to full recruitment. As such, we will apply the Pocock alpha spending function to account for the effect of this interim look on the type I error of the study. This amounts to using a significance level of 0.0294 at both the interim analysis and the final analysis, in order to maintain an overall type I error rate of 0.05.

With a total sample size of  $n = 20$  subjects, we will have 80% power at the  $\alpha = 0.05$  significance level (adjusted for two analyses with the Pocock alpha spending function) to detect a medium effect size of  $d = 0.72$ . Assuming a moderate within-subject correlation of  $\rho = 0.50$  and a standard deviation of mean fat consumption over the 60 minute treatment period of  $\sigma = 5.44$ , this translates to a detectable difference in fat consumption of 3.9%.

[figure not shown]

Figure 1: Detectable effect sizes by total sample size (A), and detectable effect sizes in terms of fat consumption assuming certain within-subject correlations (B).

[figure not shown]

Figure 2: Pilot data of energy expenditure over a two hour period for  $n = 3$  subjects.

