## **STUDY PROTOCOL**

### **Study Design**

- Crossover design
- Double-blind
- Randomized
- Primary endpoint classification: Change in fat consumption from baseline
- Secondary endpoint classification: Change in energy expenditure from baseline

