### **First Study Visit**

The first study visit for subjects who pass the screening process will require a visit to the EPARC laboratory for approximately two hours. Subjects should attend fasted from 7.30PM the previous evening, though they are allowed to continue drinking water. Subjects should not have engaged in any significant exercise for 24 hours prior to the test.

Testing will begin between 7AM and 8AM at the EPARC laboratory in the Qualcomm Institute (i.e Atkinson Hall) on the UCSD campus. A free designated parking space will be provided and laboratory staff will escort the subject into the lab where the testing takes place. Participants will have their age, height, weight and gender recorded, and undergo a 15-minute assessment of (sitting) resting energy expenditure (EE) using indirect calorimetry (COSMED, Italy) following a standardized protocol in which the subject is asked to sit quietly while watching a nature or science documentary from Netflix on a (provided) tablet computer. The subject will be fitted

with a mask that captures (and analyzes) all of their expired air to calculate oxygen uptake (VO2), carbon dioxide production (VCO2), energy expenditure (EE), and substrate (carbohydrate and fat) utilization.

The subject will then be randomized to treatment sequences via a randomized block procedure, with block sizes randomly chosen in the set {2, 4, 6}. Subjects will be assigned 1:1 between an initial active stimulation, and initial sham stimulation as a control. This will be done in a double-blind manner, and whichever group a subject is randomized to on their first visit they will crossover to the other group on their second study appointment. So if a subject is initially randomized to what happens to be the active stimulation protocol, then on their second study visit that subject will crossover and receive the sham protocol, and vice versa.

The subject will then undergo 45 minutes of either vestibular nerve stimulation or sham stimulation, as described below. The subject will continue to sit quietly watching a science or nature documentary. During this 45-minute stimulation period the subject will have their EE measured during the middle 15 minutes.

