After the 45-minute stimulation period ends the subject will remain in the EPARC facility for one more hour. They will continue to sit quietly and watch a documentary. During this 1-hour post-stimulation period the subject will undergo two more 15-minute measurements of their EE. The first 15-minute measurement will take place during the first 15 minutes of this one-hour post-stimulation period, and the second 15-minute measurement will take place during the final 15 minutes of the one-hour post-stimulation period.

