### **Specific Measure**

The Cosmed CPET, or portable K4B2, metabolic assessment unit will be used for all measurements of indirect calorimetry. Subjects are fitted with a pliable facemask that covers their nose and mouth, and allows for normal breathing. However, the facemask allows us to measure all of the air the subject inspires as well as the fractional composition of inspired and expired gases. EE and substrate utilization are derived from the VO2 and VCO2 measurements.

The primary endpoint of the study will be change in fat consumption from the baseline measurement, and the secondary endpoint will be the change in energy expenditure from the baseline.

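### The primary endpoint is change from baseline, but the SAP's t-test does not say whether it analyses levels or changes, adjusts for no baseline, and quotes a 3.9% detectable difference from an SD worded as that of a level

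*Combined protocol and SAP*

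**What the plan says.** The Study Design list gives "Primary endpoint classification: Change in fat consumption from baseline", and the Specific Measure section repeats it: "The primary endpoint of the study will be change in fat consumption from the baseline measurement". Before stimulation at each visit, subjects "undergo a 15-minute assessment of (sitting) resting energy expenditure (EE) using indirect calorimetry"; the Second Study Visit section has the same step. Each visit therefore has its own baseline.

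Three later readings follow at each visit. One is taken during stimulation: "During this 45-minute stimulation period the subject will have their EE measured during the middle 15 minutes". Two are taken afterwards: "During this 1-hour post-stimulation period the subject will undergo two more 15-minute measurements of their EE".

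SAP section 1.2 is the only analysis text. The primary test is an "independent samples t-test of differences between the first and second measurement by sequence", at 0.0294 at the n = 10 interim and at the n = 20 final analysis. Neither measurement is defined, and no baseline, change score or covariate is mentioned. For sizing, the SAP takes d = 0.72, a within-subject correlation of 0.50 and 5.44 as the "standard deviation of mean fat consumption over the 60 minute treatment period", and concludes that "this translates to a detectable difference in fat consumption of 3.9" percent.

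**The concern.** The quantity tested, the quantity used for sizing and the stated endpoint may be three different things. A visit's measurement could be the level during or after stimulation, or the change from that visit's baseline, and the two have different SDs. If changes are tested, the difference this trial can detect may be larger or smaller than 3.9%, depending on how closely a visit's baseline tracks that visit's outcome. If levels are tested, baseline information collected at both visits is left out.

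The window is open too. The SAP's 60-minute treatment period matches neither the 45-minute stimulation, which has one reading, nor the one-hour period after it, which has two readings but is not treatment. With 20 subjects and three post-baseline readings per visit, both the variable and the window should be fixed before any unblinded look.

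**Working it through.** **Inputs from SAP 1.2:** n = 20 (10 per sequence under 1:1 allocation), interim at n = 10, alpha 0.0294 per look, d = 0.72, SD 5.44, within-subject correlation 0.50. A two-sided test and no dropout are assumed, because the SAP states neither.

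**Reproducing the plan.** The two sequence means of the visit 1 minus visit 2 difference are 2δ apart, where δ is the treatment effect. The non-centrality is therefore 2δ/(SD·√(4/n)) = d·√n = 0.72·√20 = 3.22. With 18 df the power is 79.6%, and exact 80% needs d = 0.7238. At the interim (n = 10, 8 df) the power is 40.7%. The SD of the between-visit difference is 5.44·√(2·(1 − 0.50)) = 5.44, and 0.72 × 5.44 = 3.92. So 80%, 0.72 and 3.9 all reproduce, with 5.44 taken as the SD of a level.

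**Moving to the stated endpoint.** Two quantities are needed that the documents do not give:
- r, the correlation between the between-visit difference in baseline and the between-visit difference in outcome;
- k, the SD of the baseline differences divided by the SD of the outcome differences.

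With s = 5.44, the SDs are:
- level: s
- change score: s·√(1 + k² − 2rk)
- baseline-adjusted residual: s·√(1 − r²)

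The change-score SD equals the level SD when k² = 2rk, that is r = k/2. Only then does 3.9 carry over unchanged.

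**What r means.** With equal SDs and correlation 0.50 between visits for both baseline and outcome, k = 1 and r = (a − b)/(1 − 0.50) = 2(a − b). Here a and b are the same-visit and cross-visit correlations of baseline with outcome. If b = 0.50, then r = 0, 0.25, 0.5, 0.75 corresponds to a = 0.50, 0.625, 0.75, 0.875.

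**Results, k = 1, final look, alpha 0.0294.** Level and change scores use the noncentral t with 18 df. The adjusted test uses 17 df and averages over a random normal covariate, with variance factor 1 + F/(n − 2), F ~ F(1, n − 2).

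| r | Change SD | Detectable: change | Detectable: adjusted | Power at 3.92: change | Power at 3.92: adjusted |
|---|---|---|---|---|---|
| 0 | 7.69 | 5.6 | 4.1 | 48% | 77% |
| 0.25 | 6.66 | 4.8 | 3.9 | 61% | 79% |
| 0.5 | 5.44 | 3.9 | 3.5 | 80% | 88% |
| 0.75 | 3.85 | 2.8 | 2.7 | 98% | 99% |

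The level test gives 3.9 and 80% throughout. For example, at r = 0 the change SD is 5.44·√2 = 7.69, and 0.7238 × 7.69 = 5.57.

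**Sensitivity to k.** Change-score power at the same four r values is 70%, 80%, 90%, 98% for k = 0.5, and 37%, 47%, 64%, 91% for k = 1.3. Adjusted power does not depend on k.

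**Where adjustment loses.**
- Final look: about 3 points against the level test at r = 0, breaking even near r = 0.26; at most about 2 points against change scores (k = 0.5, r = 0.45).
- Interim: about 6 points against the level test at r = 0 (41% to 35%), breaking even near r = 0.39; up to about 8 against change scores (k = 0.7, r = 0.70).
- Both looks combined, simulated at 3.92 with k = 1: level 81%; change 51%, 64%, 81%, 98%; adjusted 78%, 81%, 89%, 99%.

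**Type I error.** Simulated rejection under the null was 0.029 to 0.031 at the final look and 0.051 to 0.053 over both looks, alike for all three tests.

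**The case against.** The best defence is that the protocol and SAP form one document, the endpoint is defined twice as a change, and each visit's measurement can fairly be read as its change score. On that reading baseline is already used. This stands: the SAP cannot be said to ignore baseline, only not to say whether it uses it. It does not rescue the 3.9%, because the sizing SD is still worded as that of a mean level.

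A reader might infer that the trial is badly underpowered, with 48% power and 38 subjects needed. The documents do not support that. Those figures apply only if change scores are tested and r = 0 with k = 1. With b = 0.50, that means a same-visit baseline predicts the outcome no better than a baseline from a visit at least two weeks away, which is an extreme case. If levels are tested, that loss does not arise; at r = 0.5 and k = 1, change scores give the plan's own 3.9 and 80%.

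A reader might also infer that the test is invalid. It is not: type I error is sound, and the power at d = 0.72 holds for any visit difference standardised by its own SD. Preferring regression is a matter of efficiency, and it is not better everywhere, notably at the interim.

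Finally, the text gives no unit for 5.44 and no base for the percentage, but Figure 1B, which plots detectable effects in terms of fat consumption, is not shown here and may supply them. No complaint is made on that.

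**Conclusion.** The point holds as one of specification and efficiency. The SAP does not define the variable or window it tests, has no baseline covariate, and gives a 3.9% detectable difference that is established for a level but not for the stated change-from-baseline endpoint. For changes, 3.9% holds only if r = k/2. Over r = 0 to 0.75 with k = 1, the detectable change runs from 5.6 down to 2.8, so the stated figure could err in either direction. Baseline adjustment narrows this to 4.1 down to 2.7. All of these ranges rest on r and k, which are assumptions, and on a two-sided test without dropout. The validity of the t-test and the 80% power at d = 0.72 are not in question.

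This should be changed because the remedy is cheap, not because the planned test is wrong.

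**What to change.** 1. Prespecify as primary a linear regression of the visit 1 minus visit 2 difference in fat consumption on sequence, with the visit 1 minus visit 2 difference in baseline fat consumption as covariate. The treatment effect is half the sequence difference, tested at 0.0294 at both looks. Keep the change-score t-test as a sensitivity analysis.
2. State the analysed variable and one primary window, the same at both visits: the mid-stimulation reading, the mean of the two post-stimulation readings, or the mean of all three. Reconcile it with the SAP's 60-minute treatment period. The other windows become secondary.
3. Restate the detectable difference with the SD of the quantity actually tested. If the t-test is kept as primary, say that it uses change from each visit's baseline and give the SD of that change.

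The cost is SAP wording before unblinding, no new data, and one degree of freedom (18 to 17 at the final look, 8 to 7 at the interim). The price in power is the worst-case loss shown in the working. The interim loss deserves a deliberate decision, because that look can stop the trial for efficacy.
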